1	Any large (> 20 mm) SCC lesion. Patients with large SCC lesion(s) will be referred for evaluation for surgical resection.				
2	Inoperable locally-advanced and/or non-cutaneous metastatic SCC				
3	SCC lesion(s) in cosmetically-sensitive areas (e.g., tip of nose, eyelid). If a prospective subject has SCC lesion(s) in other areas, those tumor(s) may be considered for enrollment.				
4	Taking any medication known to affect SCC growth				
5	Within the past 6 months, has used topical or systemic therapies that might interfere with the evaluation of the study medication during the study. Specifically, these include the topical use at the site of the study tumors:  Output  Glucocorticoids  Retinoids either systemically or topically at the tumor site (e.g., etretinate, isotretinoin, tazarotene, tretinoin, adapalene)  Alpha-hydroxy acids (e.g., glycolic acid, lactic acid) to the tumor site  S-fluorouracil or imiquimod:				
6	Has received treatment with systemic chemotherapy within 60 days prior to starting study medication				
7	Currently receiving systemic medications that could affect SCC tumors (e.g., oral retinoids) or might interact with remetinostat				
8	Uncontrolled intercurrent illness including, but not limited to, ongoing or active infection, recurrent seizure history or psychiatric illness/social situations that would limit compliance with study requirements				
9	Moderate to significant immunosuppression (e.g., active cancer, significant autoimmune disease) and/or receiving immunosuppressive drugs that result in moderate to significant immunosuppression (e.g., low dose oral glucocorticoids do not necessarily exclude a patient)				
10	Known or previous hypersensitivity to HDACi				
11	History of congestive heart failure, cardiac arrhythmias, or other findings of ventricular dysfunction				
12	Pregnancy or breast-feeding				

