The investigator has the right to discontinue a patient from study drug or withdraw a patient from the study at any time. In addition, patients have the right to voluntarily discontinue study drug or withdraw from the study at any time for any reason. Reasons for discontinuation of study drug or withdrawal from the study may include, but are not limited to, the following:

- Any subject who presents at screening or during treatment with a large (> 20 mm) SCC lesion: such a lesion will be discontinued from treatment (if applicable) and referred for evaluation for surgical resection. (If the patient has other, smaller lesions, these smaller lesions may be considered for enrollment in the study.)
- Subject withdrawal of consent at any time
- Any medical condition that the investigator or Sponsor determines may jeopardize the patient's safety if he or she continues in the study
- Investigator determines it is in the best interest of the patient
- Surgical or other treatment of target SCC before Week 8
- Pregnancy

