# 12.1 Statistical Design

The Primary Objective and Primary Outcome of this study is to determine if topical remetinostat will reduce SCC tumor size, as defined by at least 30% decrease in SCC tumor area (in mm²) at end of study as compared with baseline. Complete response (CR) will be defined as no clinically detectable tumor at EOS. ORR is defined as the proportion of tumors with either a complete response or a partial response (PR) among all eligible and treated lesions. Exact binomial 90% confidence intervals (CIs) will be computed for the ORR. With a planned analysis on 30 per-protocol SCCs, this study should provide 91% power to reject an ORR of 15% if the true ORR is 40% or better, at one-sided-alpha level of 0.05 with at least 9 responders.

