#### 12.4.1 Analysis Population

We will first analyze the data by intention to treat analysis and then per-protocol analysis by only including tumors ≥ 80% compliant with drug treatment. Tumors with 79% or less compliant with

drug treatment will be reported as a deviation; tumors at least 80% compliant with drug treatment will not be recorded as a deviation. Patients will be instructed to use a band-aid or other form of occlusion. If the patient has difficulty with band-aid usage, the patient may stop and this will be documented.

For subjects who drop out, we will use data from their last study visit if they contribute a biopsy. The analysis population will include participants who have consented to undergo remetinostat treatment and who have at least 1 SCC tumor.

Safety analyses will include all subjects who received at least one dose of study treatment. Graded AEs (number and percent) will be summarized and reported according to the NCI CTCAE v5.0.

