#### 12.4.2 Analysis Plan

We will analyze the overall response rate of SCC based on the change in tumor area. Objective response rate (ORR) will be defined as the proportion of tumors with either a complete response or a partial response (PR) among all eligible and treated tumors. Toxicities will be graded according to the National Cancer Institute CTCAE v5.0. Exact binomial 90% confidence intervals (CIs) will be computed for the ORR. With a planned analysis on 30 per-protocol SCCs, this study would provide 91% power to reject an ORR of 15% if the true ORR is 40% or better, at one-sided alpha level of 0.05 with at least 9 responders.

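### Large-lesion rule: 3.1 and 4.2 disagree on a patient's smaller lesions, and a lesion stopped for passing 20 mm can leave the per-protocol ORR as an uncounted failure

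*Combined protocol and SAP*

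**What the plan says.** **Eligibility.** Section 3.1 is a checklist to be completed for each subject. Its Exclusion 1 is "Any large (> 20 mm) SCC lesion. Patients with large SCC lesion(s) will be referred for evaluation for surgical resection". Nothing is added about other lesions in the same patient. Exclusion 3, on cosmetically sensitive sites, does add it: "If a prospective subject has SCC lesion(s) in other areas, those tumor(s) may be considered for enrollment".

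Section 4.2 covers a subject who has a lesion over 20 mm at screening or during treatment. It acts on the lesion: "such a lesion will be discontinued from treatment (if applicable) and referred for evaluation for surgical resection". It continues: "If the patient has other, smaller lesions, these smaller lesions may be considered for enrollment in the study".

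**Analysis.** In 12.1, "ORR is defined as the proportion of tumors with either a complete response or a partial response (PR) among all eligible and treated lesions"; 12.4.2 repeats the denominator for tumors. Section 12.4.1 plans an intention-to-treat analysis first, then a per-protocol analysis limited to tumors at least 80% compliant with treatment. Section 10.1.1 applies the same 80% limit to the primary outcome. For dropouts, 12.4.1 uses the last visit's data only where a biopsy was contributed. It defines the population by consent and tumor: "The analysis population will include participants who have consented to undergo remetinostat treatment and who have at least 1 SCC tumor". Neither 10.1.1 nor 12.4.1 mentions the 20 mm limit or says how a lesion stopped for growth is scored.

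The synopsis targets 30 per-protocol evaluable tumors and does not count subjects who contribute none. Section 12.6.2 bases the power and the 9-responder rule on those 30.

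**The concern.** There are two separate problems.

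First, site staff have two instructions for a patient with one lesion over 20 mm and another below it. Read as a line in a subject-level checklist, Exclusion 1 keeps the patient out. Section 4.2 lets the smaller lesion in. Because the ORR denominator refers to eligible lesions, the word needs one meaning.

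Second, and more important for the endpoint, a study lesion that grows past 20 mm on treatment is a treatment failure. Stopping its treatment can also make it non-compliant, and the per-protocol set excludes non-compliant tumors. Since accrual aims at a fixed number of per-protocol tumors, the failure can be replaced by a new tumor with its own chance of responding. The per-protocol ORR is then biased upward.

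**Working it through.** **1. The eligibility passages side by side.** Take a patient with a 22 mm and an 8 mm SCC (an illustration). Under 3.1, Exclusion 1 is met and no carve-out applies. Under 4.2, the 22 mm lesion is referred and the 8 mm lesion may be considered. No other section settles which rule prevails.

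**2. The plan's own figures.** Inputs from 12.6.2: n = 30, null ORR 15%, alternative 40%, success at 9 or more responders, one-sided alpha 0.05. Exact binomial, tumors treated as independent:
- Power: P(X ≥ 9 | 30, 0.40) = 0.906, matching the stated 91%.
- Type I error: P(X ≥ 9 | 30, 0.15) = 0.0278. With a cut-off of 8 it would be 0.0698, so 9 is the smallest valid cut-off.

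These figures depend only on n and the cut-off, so neither problem alters them.

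**3. When a stopped lesion falls below 80%.** The plan does not define the compliance denominator. Assume the planned 8 weeks = 56 days, with full adherence until treatment stops. Then compliance = d/56, and 0.80 × 56 = 44.8, so 45 full days are needed.
- The scheduled measurement during treatment is Week 4 ± 1 week (section 9). Stopping then gives 21/56 = 37.5% to 35/56 = 62.5%, and 28/56 = 50% at Week 4 itself. All are below 80%.
- A lesion first found over 20 mm after day 45, for example at the Week 10 visit, can still be compliant.
- Other denominators: if only days up to the stop are counted, the lesion can remain compliant. If the optional 12 weeks (84 days) is used, the threshold is 0.80 × 84 = 67.2 days.

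**4. Size at the decision boundary.** Start from 9/30 per-protocol and restore k excluded failures as non-responders. The exact 90% lower limit is the 5% quantile of Beta(x, n − x + 1); p = P(X ≥ 9 | n, 0.15).

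| k | Result | ORR | Lower limit | One-sided p | 15% excluded? |
|---|---|---|---|---|---|
| 0 | 9/30 | 30.0% | 16.6% | 0.028 | yes |
| 1 | 9/31 | 29.0% | 16.1% | 0.034 | yes |
| 2 | 9/32 | 28.1% | 15.5% | 0.041 | yes |
| 3 | 9/33 | 27.3% | 15.03% | 0.0495 | yes |
| 4 | 9/34 | 26.5% | 14.6% | 0.059 | no |

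It takes four such lesions to reverse a result exactly at the cut-off.

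**The case against.** **Exclusion 1 names a lesion and never says in words that the patient is ineligible.** Section 4.2 addresses the screening case expressly and could be read as completing it. This stands as a possible reading: the patient-level reading is natural, given the checklist format and the contrast with Exclusion 3, but it is not stated. That is a reason to reconcile the wording, not to leave it.

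**Intention to treat comes first, over all eligible and treated lesions.** A lesion within the size limits at entry, then treated, should stay in that denominator as a failure. This stands in part. The biopsy condition for dropouts weakens it, because section 6 takes subjects who discontinue treatment off study and biopsies depend on consent. The power and the 9-responder rule are also stated for the per-protocol tumors.

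**Losing failures is a general feature of the 80% rule.** It can also follow from the 30% growth rule at Week 4 and from toxicity stops in 6.1. That is correct; the 20 mm rule is one route among several, and it does not arise from the mismatch between 3.1 and 4.2.

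**Stronger readings that a reader might infer.** One is that the mismatch lets eligibility be settled once response is known. The documents do not support this: 3.1 requires the checklist to be completed, signed and dated, with completion before registration, and an independent reviewer to verify eligibility. A patient excluded at that point is not treated and so never enters the denominator. Another is to size the problem by removing a responder from 9/30. That does not fit the mechanism, since a lesion stopped for growth is a non-responder, and a tumor ruled ineligible during accrual could be replaced.

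**Conclusion.** Both problems hold, with limited reach. Sections 3.1 and 4.2 conflict on the natural reading of Exclusion 1 and must be reconciled; the documents do not show which rule was intended.

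The on-treatment problem bears on the endpoint. A lesion stopped for passing 20 mm before about day 45 leaves the per-protocol ORR although it has failed, and can be replaced. The direction of bias is upward. The size is unknown because the plan gives no expected number of such lesions. At the 9/30 boundary, up to three leave the conclusion intact and four reverse it. Results further above the cut-off would need more.

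This rests on a 56-day compliance denominator, full adherence until the stop, independent tumors, and a lesion past 20 mm not also having lost 30% of its area. It does not follow that the planned sample size, power or alpha are wrong, or that eligibility can be chosen after the outcome.

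**What to change.** 1. Reconcile 3.1 and 4.2 to one rule. If patient-level, remove the allowance for smaller lesions from 4.2. If lesion-level, add to Exclusion 1 a carve-out on the pattern of Exclusion 3. The choice belongs to the investigator and sponsor. Make the meaning of eligible in 12.1 and 12.4.2 follow it.

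2. Add to 12.4.1: a treated study lesion discontinued because it grew past 20 mm stays in the denominator as a non-responder in both the intention-to-treat and per-protocol ORR, whatever its compliance and whether or not a biopsy is contributed. This works under any compliance denominator. It changes scoring only, not when treatment stops.

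3. Say whether such a lesion counts toward the 30. If it does, the 9-of-30 rule stands. If it is added on top, the smallest valid cut-off stays at 9 up to n = 33 and becomes 10 at n = 34.

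The cost is a few sentences and a slightly lower ORR where such lesions occur. No added visits or data are needed.

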# HDAC inhibitors are well-tolerated and have resulted in promising clinical responses in patients with advanced stage head and neck squamous cell carcinoma

A phase 1 study of 26 patients with advanced stage head and neck SCCs of mixed etiology demonstrated similar to more-favorable safety and tolerability profiles when compared to pre-existing chemoradiation regimens that did not include a HCAC inhibitor. While clinical response to therapy was not the primary endpoint of this phase 1 study, encouraging tumor responses were observed despite the subjects' advanced-stage tumors.

Altogether, the preliminary data suggests HDAC inhibitors are a promising new candidate therapy for SCC.

Remetinostat is a novel histone deacetylase inhibitor (HDACi) that was designed with a metabolically-labile ester bond so that topical application would produce effective local histone deacetylase (HDAC) inhibition in cutaneous lesions while resulting in only negligible systemic HDAC inhibition. Remetinostat is rapidly degraded into primary metabolites SHP-100 and methylparaben. Three studies (an *in vitro* Franz Diffusion Cell assay; a 28-day study in minipigs; and a 90-day study in minipigs) showed that uptake of remetinostat through skin into the systemic circulation was minimal. In both dermal and intravenous (IV) studies in animals, remetinostat was metabolized in the blood rapidly to the primary metabolites. These findings suggest that dermal application of remetinostat largely obviates systemic exposure to the HDAC inhibitor remetinostat and, consequently, sequelae from systemic inhibition of HDAC. This observation was supported by the fact that in a Phase 1 study in patients with cutaneous T-cell lymphoma (CTCL), plasma concentrations of remetinostat were minimal and at or below the lower limit of quantitation of the assay indicating minimal systemic exposure. The lack of measurable levels of remetinostat in blood is consistent with the rapid conversion of remetinostat to its metabolites.

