Remetinostat has been tested in a battery of safety pharmacology studies. Remetinostat did not affect the functional observational battery (FOB) parameters in rats given IV doses of up 100 mg/kg/day, which is equivalent to a dose of approximately 970 mg in a 60-kg human subject. Remetinostat also did not inhibit human ether à-go-go-related gene (hERG) current *in vitro* at concentrations up to approximately 32,000 ng/mL and did not affect cardiovascular function in minipigs given IV doses of up to 100 mg/kg, which is equivalent to a dose of approximately 5,700 mg in a 60-kg human subject. Based on the lack of effect observed in these studies, it was anticipated that remetinostat would be unlikely to adversely affect nervous system or cardiovascular system function when administered topically to humans. This observation has been supported by the clinical data, to date.

A program of Good Laboratory Practice (GLP) - compliant toxicity studies evaluated the safety of multiple doses of remetinostat administered IV to rats and administered topically to minipigs. In addition, the genotoxicity of remetinostat and the local tolerance and sensitizing potential of remetinostat and placebo gel solutions were assessed. Remetinostat and placebo gel were tolerated, with only excipient-related local irritation when applied topically, and renal histopathologic changes not relevant in humans when administered IV. The 28-day No-Observed-Adverse-Effect-Level (NOAEL) for remetinostat administered IV to rats was

30 mg/kg/day. When remetinostat gel 1.5% was applied topically in minipigs, the 28-day and 90-day NOAEL of 150 μg/cm² of skin yielded a total dose of approximately 6 mg/kg.

Based on these findings, a phase 1 (SHP-141-001) study was conducted (NCT01433731) in 18 patients with stage IA-IIA MF-CTCL. This randomized, double-blind, placebo-controlled dose-escalating study was designed to evaluate the safety, pharmacokinetics and pharmacodynamics of remetinostat gel administered topically twice-daily up to 28 days in patients. Escalating doses of remetinostat gel, 0.1%, 0.5% and 1%, were administered BID for a maximum of 28 days to 3 cohorts of patients (n = 6 patients per cohort, active:placebo ratio 5:1).

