#### 5. INVESTIGATIONAL DRUG INFORMATION

#### 5.1 Investigational Drug

Remetinostat is also known as suberohydroxamic acid phenyl ester (SHAPE); SHAPE Gel; SHP-141; and 4-[[8-(hydroxyamino)-1,8-dioxooctyl]oxy]-benzoic acid methyl ester. Remetinostat is a histone deacetylase inhibitor (HDACi) that was designed with a metabolically-labile ester bond so that topical application would produce effective local histone deacetylase (HDAC) inhibition in cutaneous lesions while resulting in only negligible systemic HDAC inhibition.

In this single-arm study, remetinostat is formulated at a strength of 1.0% in a gel consisting of dehydrated alcohol; propylene glycol; hexylene glycol; glycerin; oleyl alcohol; diisopropyl adipate; hydroxypropylcellulose; butylated hydroxytoluene and citric acid (anhydrous). The overall concentration of ethanol in the gel is approximately 50% (w/w). The primary packaging for remetinostat gel is aluminum tubes with plastic screw-on caps. The 60-g tubes are packaged in paper cartons (both labeled with identical labels).

See the remetinostat Investigator Brochure for additional information including the mechanism of action; summaries of animal and clinical studies; non-clinical and clinical pharmacokinetic; major route of elimination; safety profile; and the non-clinical and clinical data supporting the dose and regimen chosen for this study.

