#### 7. ADVERSE EVENTS AND REPORTING PROCEDURES

#### 7.1 Potential Adverse Events

Slight irritation of the skin was observed in some animal studies and was likely related to the ethanol in the formulation.

Escalating doses of remetinostat gel were administered to different cohorts of patients to assess safety and tolerability in a Phase 1 study in patients with CTCL. A total of 18 patients with CTCL were sequentially enrolled into one of three study cohorts consisting of six patients each. Within each study cohort of six patients, 5 were randomly assigned to receive remetinostat gel and 1 was randomly assigned to receive placebo. Patients received treatment for a maximum of 28 days. Three dose levels of remetinostat gel were evaluated at 0.1%, 0.5% and 1%.

The study drug was well-tolerated. Eight patients, including one who received placebo, experienced 11 treatment-related adverse events. The adverse events consisted of a skin burning or warming sensation, paraesthesia, and contact dermatitis and were all related to topical application of study drug to the index lesion treatment sites. Ten of the treatment-related

adverse events were mild (Grade 1) and one event (contact dermatitis) was Grade 2. Only the Grade 2 event of contact dermatitis required treatment, for which topical steroid and moisturizer were applied after the patient completed the 28-day course of remetinostat gel treatment, which resolved. All treatment-related adverse events had resolved prior to the Day 42 End-of-Study visit.

There were no hematological findings among the 18 treated patients. Among the 5 clinical laboratory changes reported as adverse events and the 4 clinical laboratory values that reached ≥ Grade 2, none was related to study drug administration.

For the phase 2 study, 60 patients were randomised in a 1:1:1 ratio to three treatment regimens of remetinostat gel (1% QD, 0.5% BID and 1% BID). Patients received treatment for 6 months and could continue on treatment for a further 6 months (12 months in total) if they received clinical benefit during the first 6-month period.

Remetinostat gel at dosing regimens of 1% QD, 0.5% BID and 1% BID was generally well tolerated, with no reports of adverse events associated with systemic HDAC inhibitors. There were 2 SAEs (acute heart failure and fracture), observed during the study, considered unrelated to treatment with remetinostat.

The most common adverse events were pruritus and skin irritation.

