Approximately half of the patients in each group reported AEs considered related to treatment; 4 of these met CTCAE Grade ≥ 3 for severity and all were skin-related: The rate of discontinuations due to treatment-related AEs was low, with no indication of a higher rate in the highest (1% BID) dose group. Overall, the patients who had dose reduction/interruptions due to remetinostat related skin AEs in the 1% BID dose group stayed on treatment for a long time. The CTC Grade 3 events resolved, patients wanted to stay on treatment despite these AEs (except for a single patient) and most of the patients (4 of 6) in this highest dose group who remained on drug for > 6 months received benefit, in terms of objective CAILS and/or pruritus responses.

In the current study, skin will be carefully evaluated during treatment. Patients who develop contact dermatitis caused by the strip bandage adhesive per PI determination may discontinue bandage use.

No systemic abnormalities were found at any dose level in the nonclinical studies and no treatment-related observations other than those above were noted in any clinical trial. Thus, no special precautions are anticipated.

The effect of remetinostat in pregnancy has not been studied. Similarly, excretion of remetinostat into breast milk has not been examined. Therefore, pregnant and lactating women are excluded from clinical trials at this time.

Remetinostat is considered unlikely to be a photo-irritant as remetinostat absorbs light at a maximum of 234 nm in the UV/visible spectrum and does not meaningfully absorb light above 290 nm. Photo-irritation has not been observed in clinical trials of remetinostat gel. There is no information to indicate that abuse or dependency would occur with exposure to remetinostat gel.

Detectable systemic levels of remetinostat after topical application are not anticipated.

See the Investigator Brochure for details on AEs captured to date from CTCL study.

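### Exclusion 10 covers allergy to HDAC inhibitors only, not to the listed gel ingredients or the named metabolite methylparaben

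*Combined protocol and SAP*

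**What the plan says.** Exclusion 10 in section 3.1 reads "Known or previous hypersensitivity to HDACi". It is one of 12 numbered exclusions and the only one that mentions allergy.

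Two other places describe what a subject will be exposed to:

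- Section 5.1 lists the gel base: dehydrated alcohol, with ethanol making up about half the gel by weight, and then "propylene glycol; hexylene glycol; glycerin; oleyl alcohol; diisopropyl adipate; hydroxypropylcellulose; butylated hydroxytoluene and citric acid (anhydrous").
- Section 2.2 (Study Agent, under the sub-heading on tolerability of HDAC inhibitors) states: "Remetinostat is rapidly degraded into primary metabolites SHP-100 and methylparaben".

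On local reactions, section 2.2 reports that the topical toxicity studies were tolerated "with only excipient-related local irritation when applied topically". Section 7.1 says that slight irritation in some animal studies "was likely related to the ethanol in the formulation", and that among the treatment-related events of the phase 1 lymphoma study "one event (contact dermatitis) was Grade 2". Section 7.1 concludes that no special precautions are expected to be needed.

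**The concern.** An allergy exclusion in a trial of a topical product would normally cover the product as applied, not just the pharmacological class of its active ingredient. Here the criterion stops at the class. A coordinator who follows the checklist literally has no line on which to record, or act on, a known allergy to a gel constituent or to methylparaben.

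What is at stake is a small, avoidable safety risk. Someone whose allergy is already documented could be enrolled and instructed to apply the substance repeatedly under a dressing. The issue is limited to allergies known at screening. It does not extend to reactions that could not have been foreseen.

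**Working it through.** No formula applies, because the point is about the scope of a criterion. The check sets the exposures that the protocol names against the criteria meant to screen for them.

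**1. Exposures named in the protocol, and whether an entry criterion covers known allergy to them**

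| Exposure | Where named | Covered at entry? |
|---|---|---|
| Remetinostat, an HDAC inhibitor | 2.2, 5.1 | Yes, Exclusion 10 |
| Nine listed gel constituents (dehydrated alcohol plus the eight quoted above) | 5.1 | No |
| Methylparaben, a primary metabolite | 2.2 | No |

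**2. The other exclusions.** The remaining 11 concern lesion size, disease extent and site, medication that affects SCC, earlier topical or systemic treatment, chemotherapy, systemic drugs that could affect the tumors or interact with remetinostat, intercurrent illness, immunosuppression, cardiac history, and pregnancy or breast-feeding. None can reasonably be read as covering contact allergy to a gel constituent.

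**3. Planned exposure.** Section 4 specifies application three times daily for 8 weeks under a bandage: 3 × 7 × 8 = 168 applications. This describes the length of contact, not the risk.

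**4. When the existing safeguards act**

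- Section 6.1 and Table 1 require suspension from Grade 3 local dermal irritation upward, and withdrawal if it has not improved to Grade 2 or lower within 2 weeks. Both need a reaction to have occurred.
- Section 4.2 lets the investigator discontinue or withdraw any patient at any time. That is a power over people already in the study, not an entry criterion.

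So neither provision prevents the first exposure of a person with a known allergy.

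**5. Effect on the design figures.** The plan states 91% power with at least 9 responders among 30 tumors, 15% against 40%, one-sided alpha 0.05. For X binomial with n = 30:

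- P(X ≥ 9) at 15% = 0.0278
- P(X ≥ 9) at 40% = 0.906

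The stated power is reproduced. Its inputs are 30, 9, 15% and 40%, and none depends on the wording of Exclusion 10.

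**6. What cannot be computed.** The documents do not give the frequency of known allergy to any of these substances. Nor do they say whether the earlier remetinostat studies excluded such people. The earlier tolerability data therefore neither measure this risk nor rule it out.

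**The case against.** The case against acting has several parts, and some of it stands.

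*Irritation is not allergy.* Sections 2.2 and 7.1 describe irritation from excipients or ethanol, and an allergy question would not be expected to prevent that. Section 2.2 also says that sensitizing potential was assessed, and it describes no sensitization finding. This stands. The irritation passages are not evidence that the constituents cause allergy, and the phase 1 contact dermatitis is not attributed to any component. The point rests only on the mismatch between what the subject is exposed to and what the checklist asks.

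*Methylparaben appears only as a metabolite.* This also stands. The documents do not call it an irritant or an allergen and do not give its level in skin. A reader might infer that they identify it as a hazard, but they do not. It belongs in the criterion only because the protocol names it as something the drug becomes.

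*Allergy to the dressing adhesive.* A reader might infer that this is a third gap. It is not: section 4 allows paper tape with a non-adherent dressing, section 7.1 provides that "Patients who develop contact dermatitis caused by the strip bandage adhesive per PI determination may discontinue bandage use", and section 12.4.1 lets a patient who has difficulty with the bandage stop it, with documentation. An exclusion would turn away people whom the protocol already accommodates.

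*Damage to the endpoint.* A reader might also use the protocol's earlier data to size the problem: 10 of 60 phase 2 lymphoma patients (2 + 2 + 6) stopped for drug-related events, and 10 of 14 in the basal cell carcinoma series had an eczematous reaction. Neither figure measures allergy. The first counts drug-related events without attributing any to allergy. The second comes from a six-week course with Grade 1-2 reactions, below the level at which Table 1 requires suspension. The documents do not show that reactions in people with known allergy would distort tumor measurement or the response rate.

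*Treatment continues for 8 weeks whatever happens.* The documents do not support this reading either, given the suspension, withdrawal and discretion rules.

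After all this, one thing is unanswered: every safeguard cited for the gel itself comes after the first application.

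**Conclusion.** The point holds in a narrow form. In the visible criteria, Exclusion 10 is limited to HDAC inhibitors, so a person with a documented allergy to a constituent listed in 5.1, or to methylparaben as named in 2.2, is eligible as written. Severity is low: this is an optional safety improvement, with no effect on power, alpha, sample size or the analysis.

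The size of the risk cannot be stated, because the documents do not give the frequency of such allergy. The conclusion assumes that no further criterion or warning appears on the page after the exclusion list or in the Investigator Brochure, neither of which could be consulted. It also assumes that staff apply the checklist literally. A careful investigator might well decline such a person without being told to, but nothing in the visible text asks for that.

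**What to change.** Bring Exclusion 10 into line with sections 5.1 and 2.2, so that it covers known or previous hypersensitivity to the study gel: an HDAC inhibitor, any ingredient listed in section 5.1, or the metabolite methylparaben. Leave the adhesive out, since sections 4, 7.1 and 12.4.1 already deal with it. First check the page after the exclusion list and the Investigator Brochure; if either already carries such a criterion, a cross-reference in the checklist is enough.

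The cost is one reworded checklist line, submitted as a protocol modification under section 11.1. It can be answered from the medical history that the study calendar already schedules before treatment, with no new test or visit. The downside is that a few people with known contact allergies will be screened out.
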